Removal and Refusion				

E. Baseline and Operative Analysis

Baseline summaries will be chosen to be appropriate for the scale and distribution of the measures being analyzed. Statistical methods will be the same as described above for the non primary endpoint analyses.

F. Missing data

Except for the primary analysis, if a value, at any assessment is not available for analysis, it will be excluded from summaries.

G. Study Hypothesis and Sample Size Determination using a Literature Control

Study Hypothesis

The hypothesis is Dynesys fusion rate is non-inferior to the historical literature sample data estimated fusion rate of 80.6%. This hypothesis will be assessed by testing that the difference between the experimental rate (p_e) and the historical control rate (p_c) is not worse than 10%. The non-inferiority test will be inferred if the lower limit of the 95% confidence interval around the **treatment difference** between 2 groups is greater than $\delta = -10\%$.

$$H_0: p_e - p_c \leq -0.10$$

$$H_1: p_e - p_c > -0.10$$

Sample Size

Sample size for the Dynesys Post-Market Surveillance Study was estimated using SAS, Proc Power with a testing level alpha (Type I) error level of 0.05, 80 percent statistical power, a meaningful difference of 10%, and a success rate for lumbar fusion from the literature historical

control group of 80.6% (0.806). For this set of criteria, the sample size was 134, without adjustment for attrition. With a 20% attrition sample added, this would result in a sample size of 168.

Sample size estimates are presented in Table 2.

Table 2: Proposed Sample Sizes

Primary Endpoint	Difference	Predicted Success	Type I Error	Power	N Patients
Radiographic Success (Fusion)	10%	80.6%	0.05	80%	168

VI. TIMELINE

A. Clinical Trial Agreement

No portion of this protocol will be implemented until both copies of the Clinical Trial Agreement have been completed by both parties.

Table 3: Study Timeline

Study Timeline	Sponsor Expectation
Expected date of Study Initiation	March 2012
Expected date of first IRB Approval(s)	January 2012
Expected monthly number of sites obtaining IRB approval	1
Expected subject enrollment initiation	March 2012
Expected average number of subjects to be enrolled/month	7
Expected Date of Subject Enrollment Completion	March 2014
Expected date of Subject follow-up Completion	March 2016
Reports	
Interim Postmarket Surveillance Study Report	Every 6 months through 2 years, annually thereafter
Expected date for the Final Postmarket Surveillance Study Report	June 2016

B. Institutional Approvals

No portion of this protocol will be implemented until approval is granted by the institutional review board. No personal health information or other data will be transmitted to Zimmer Spine without consent from the patient.

C. Project Execution

This project will begin at the time of contract agreement execution. IRB approval will be obtained within 2 months. Enrollment will start following IRB approval and site initiation. The first patient will be enrolled within 2 months after IRB approval. Enrollment will take place for 24 months. Follow-up of all patients will be complete within 26 months (24 months +/- 2 month visit window) following the last surgery.

D. Project Deliverables

The site must provide Zimmer Spine with a copy of the report submitted to the IRB for annual renewal and the approval status within two weeks of receipt. The report must include the number of patients enrolled and the treated levels.

E. Monitor Schedule

This study will be monitored a minimum of one time every 12 months by Zimmer Spine Clinical Affairs personnel per the Zimmer Spine monitoring procedure. The purpose of these visits is to review the patient charts, to verify the data submission process, and to clarify any discrepancies. With increased enrollment or center challenges, monitoring may occur more than once a year.

F. Record Retention

The investigator will maintain the records of the study including all correspondence, the study protocol with any/all amendments, all correspondence with and approval from the IRB, the budget agreement, the research agreement, individual patient records, and signed informed consent forms. Patient files and other source data must be kept for a period of not less than 2 years after the date on which this investigation is terminated or completed.

G. Final Reports

A final report produced by the lead principal investigator will be written in a format acceptable for a peer reviewed journal.

H. Termination of Study

The study may be terminated per the terms of the Clinical Trial Agreement at any time.

**Appendix A:
EXPLANT ANALYSIS PROTOCOL**

**Appendix B:
IMAGING PROTOCOL**

**Appendix C:
INSTRUCTIONS FOR USE**

The Instructions for Use as provided in the January 21, 2010, response to FDA will be used and are not repeated here.

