E. Post-Operative – Annual Visits after 24 month until all patients have completed the study (+/- 8 weeks)

The following procedures and assessments will be performed following surgery.

- *Patient Assessment*: pain level and satisfaction
- *Oswestry Disability Index (ODI)*: functional assessment
- *Clinician Evaluation*: neurological assessment (sensory and motor testing, reflex testing and straight leg raising), medication usage, employment status, tobacco use and surgical results
- *Radiographs*: A/P, N/L, flexion, extension
- *Radiographic Assessment*: overall and unilateral fusion success (translation motion <3mm, angulation motion <5° and bridging bone) will be assessed by site radiologist and an independent reviewer
- *Adverse Event*: record events, device relationship, date of complication, severity, outcome and treatment details
- *Protocol Deviation* (as needed): deviation and reason
- *Patient Discontinuation* (as needed): reason for discontinuation and date

F. Interim or Unscheduled Visits

- *Adverse Event*: record events, device relationship, date of complication, severity, outcome and treatment details
- *Explanted Device Form (as needed)*: date and reason for explant
- *Protocol Deviation* (as needed): deviation and reason
- *Patient Discontinuation* (as needed): reason for discontinuation and date

G. Adverse Events (AE)

An adverse event is any unfavorable and unintended sign, symptom, or disease associated with the use of an investigational product, whether or not related to the investigational product, taking into consideration the patient history, surgical history, histological analysis as well as explants evaluation. Events may be complications, observations (including radiographic), change in patient condition or related/unrelated death. A change indicating worsening as reported on an assessment is an adverse event.

A serious adverse event (SAE) is any event that is fatal, life-threatening, disabling, or which results in hospitalization.

A unanticipated adverse device effect (UADE) is defined as any serious adverse effect on health or safety, or any life-threatening problem or death caused by, or associated with, a device if that effect, problem or death was not previously identified in nature, severity or degree of incidence, or any other unanticipated serious problem associated with a device that relates to the rights, safety, or welfare of subjects.

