The investigator will complete the Adverse Events case report form to capture:

- Date and time of onset of the event
- Type of complication
- Severity
 - **Mild:** The AE is noticeable to the subject, but does not interfere with routine activity. The AE typically does not require symptomatic therapy, rest or device removal.
 - **Moderate:** The AE interferes with routine activity but responds well to symptomatic therapy or rest. The AE does not require device removal.
 - **Severe:** The AE significantly limits the subject's ability to perform routine activities despite symptomatic therapy. The AE requires medical or surgical treatment or results in hospitalization. In addition, the AE may require removal of the study device.
- Relationship to the device
 - **Not related:** An AE for which sufficient information exists to indicate that there is no causal connection between the event and the device/procedure. The AE is due to and readily explained by the subject's underlying disease state or is due to concomitant medication or therapy not related to the use of the device or the procedure.
 - **Possibly related:** There is a reasonable possibility that the AE may have been primarily caused by the device/procedure and follows a known or expected response pattern. Alternative etiology is equally or more likely compared to the potential relationship to the use of the device/procedure.
 - **Probably related:** There is a reasonable probability that the AE may have been primarily caused by the device/procedure and follows a known or expected response pattern.
 - **Definitely related:** The AE has a strong causal relationship to the device/procedure and follows a known response pattern. The event cannot be

reasonably explained by known characteristics of the subject's clinical state or other therapies.

- Treatment includes a detailed narrative of how this adverse event was treated and the outcome.

The outcome of the event will be defined as resolved, ongoing, study withdrawal, device revision, removal, reoperation, supplemental fixation and death. Additional surgeries will include details in the treatment narrative.

- **Revision:** a procedure that adjusts or in any way modifies or removes part of the original implant configuration, with or without replacement of a component. A revision may also include adjusting the position of the original configuration.

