- **Removal:** a procedure where the entire original system configuration is removed with/without replacement.*
- **Reoperation:** any surgical procedure at the involved level(s) that does not involve removal, modification or addition of any components to the system.
- **Supplemental Fixation:** a procedure in which additional instrumentation not under study in the protocol is implanted at the spine level(s) under study.

* Elective removals following fusion are not considered adverse events; however, they will still be reported.

All adverse events observed during the course of this study, regardless of severity or relationship to the investigational device will be recorded on the Adverse Event case report form. All events should be followed until resolved or until a chronic, stable state is achieved.

All serious adverse events and unanticipated adverse device effects or events of unexpected severity must be reported to Zimmer Spine within 24 hours of the time the investigator learns of the event or effect. Zimmer Spine will notify the reviewing IRBs within 10 days of the time of learning of the event.

H. Adverse Events Advisory Group

Independent spine surgeons (neuro or orthopedic) will be selected from a subset of 13 member (10 US and 3 OUS) Zimmer Spine Clinical Affairs Advisory Group (CAAG), who are not study investigators, to determine adverse event severity and device relationship.

The CAAG surgeons serve two-year terms and function to provide expert advice to the Clinical Affairs department with respect to protocol development, unmet clinical needs, clinical benefits of devices, quantification and measurement of clinical evaluations, pathology, diagnosis and indication and review of explant cases during clinical trials. The surgeons have a strong core competency in the conduct and logistics of clinical trials. This group allows Zimmer Spine the ability to quickly and responsibly respond to any questions regarding clinical use of our devices, review of data from clinical trials and response to other research collaborators with respect to study conduct. The members of this panel can be trained on the protocol, most importantly, with respect to the blind adjudication of adverse events determining severity and relatedness. The depth of the panel allows

Zimmer Spine to easily convene three members for adjudication and receive expert assistance in review of any adverse events that may ultimately be “unanticipated” or “serious.”

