The adjudication process will occur at least annually during the study. Reviewers will be blinded to the site. Two independent surgeons will review all available appropriate data (including CRFs, AE forms, hospital operative reports, lab reports, films, discharge reports, etc.) and determine:

- whether the event is related to the device, device procedure, general surgery; or none of the above
- AE severity (mild, moderate, severe)
- whether the event constitutes a SAE or UADE.

In instances of non-concordance between the two surgeons, a third surgeon will provide the final determination. The surgeons will provide their review, adjudication and reporting independent of the trial.

All reviewing surgeons' determinations regarding the AEs are final and supersede preliminary judgments made by each clinical investigator.

The sponsor has the responsibility for coordinating the adjudication process. All correspondence, reports, minutes and other documentation as applicable will be supplied to the FDA as part of the regular progress reports.

The sponsor will notify regulatory authorities (FDA, IRB, etc) and the clinical study investigators of any SAE/UADEs in accordance with regulations.

I. Explant Analysis

All hardware segments, complete constructs or components must be returned to Zimmer Spine for analysis by the site using the explant kits provided at the initiation training. Instructions and all necessary materials for returning the hardware will be included in the explant kit. Investigators and external Zimmer representatives will be trained on the importance and process of returning explants for analysis.

Every attempt will be made to evaluate the explanted devices using the Analysis of *Dynesys* Explants Protocol (Appendix A). A secondary analysis to determine the association (if any) between demographics, clinical data, device failure and characteristics will also be completed.

J. Patient Withdrawal

A patient is enrolled in the study by signing a Zimmer Spine, Inc., IRB approved informed consent. No personal health information will be collected from the patient prior to obtaining a signed informed consent.

Patients who are determined to be ineligible prior to surgery will be considered screen failures and will not require additional follow-up visits. The reason(s) for ineligibility will be documented on the Patient Discontinuation case report form.

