2.3 Complications and Possible Adverse Events

Prior to surgery, patients should be made aware of the following possible adverse effects in addition to the potential for additional surgery to correct these effects:

- Loosening, disassembly, bending or breakage of components;
- Tissue sensitivity to implant material;
- Potential for skin breakdown and/or wound complications;
- Non-union or delayed union;
- Infection;
- Nerve damage, including loss of neurologic function, dural tears, paralysis, paresthesia, and cerebral spinal fluid leakage;
- Fracture of vertebrae;
- Foreign body reaction (allergic) to components or debris;
- Loss of fixation;
- Vascular or visceral injury;
- Change of normal spinal curvature;
- Gastrointestinal, urological and/or reproductive system compromise;
- Pain or discomfort;
- Bursitis;
- Decrease in bone density due to stress shielding;
- Loss of bone or fracture of bone above or below the level of surgery;
- High removal torques may be encountered with the use of the hydroxyapatite coated screw;
- Bone graft donor site pain, fracture, and/or delayed wound healing;
- Restriction of activities;
- Lack of effective treatment of symptoms for which surgery was intended;
- Death.

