- 3 = hyperesthesia

--	--	--

Patient Initials

--	--	--	--	--	--	--

Patient ID

--	--	--

Investigator ID

Date of Surgery

--	--

 -

--	--

 -

--	--	--	--

(MM-DD-YYYY)

Form Completion Date

--	--

 -

--	--

 -

--	--	--	--

Straight Leg Raising

Not Completed	Right	Not Completed	Left
	 0  1		 0  1

Straight Leg Raising Scores

0 = positive
1 = negative

Reflex Testing

Not Completed	Right	Not Completed	Left
Patella	 0  1  2	 0  1  2	 0  1  2
Achilles	 0  1  2	 0  1  2	 0  1  2

Reflex Scores

0 = absent
1 = abnormal (increased or decreased)
2 = normal

12. Discharge Medications for Back or Leg Pain: (Check all that apply)

- None
- Muscle Relaxant
- Narcotic
- Non-Narcotic Analgesic
- Non-Steroidal Anti-inflammatory
- Steroidal Anti-inflammatory
- Other, specify:

13. Reason for Device Construct Used: (Check all that apply)

- Pathology
- Diagnosis
- Patient Anatomy
- Surgeon Preference
- Other, specify:

14. Were there any intraoperative or immediate postoperative complications? Yes No

If Yes, please complete Adverse Event Form.

15. Were there any device malfunctions? Yes No

If Yes, please complete Adverse Event Form.

Investigator's Signature:

Date:

--	--

 -

--	--

 -

--	--	--	--

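### The SAE definition omits prolonged hospital stay and surgical intervention, so some anticipated index-stay complications and repeat procedures miss expedited reporting

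*Combined protocol and SAP*

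**What the plan says.** Section IV.G defines seriousness in one sentence: "A serious adverse event (SAE) is any event that is fatal, life-threatening, disabling, or which results in hospitalization". The reporting duty later in the same section is: "All serious adverse events and unanticipated adverse device effects or events of unexpected severity must be reported to Zimmer Spine within 24 hours". The sponsor then notifies the reviewing IRBs within 10 days of learning of the event. Under Section IV.H it also notifies regulators and study investigators of SAEs and UADEs.

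Three other parts of the plan bear on the point.

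- **Severity grades (IV.G).** The Severe grade includes this sentence: "The AE requires medical or surgical treatment or results in hospitalization". The grade is not itself a trigger for the 24-hour report.
- **Further surgery (IV.G).** Revision, removal, reoperation and supplemental fixation are defined as outcomes of an adverse event. Reoperation, for example, is "any surgical procedure at the involved level(s) that does not involve removal, modification or addition of any components to the system". None of the four is a seriousness criterion.
- **Adjudication (IV.H).** Two surgeons, with a third for disagreements, decide among other things "whether the event constitutes a SAE or UADE". IV.H gives no separate definition of an SAE, and adjudication is required at least annually.

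**The concern.** The study exposure is spinal surgery on an admitted patient; the Operative/Discharge Evaluation records admission and discharge dates. A patient already in hospital is not, in the ordinary sense, hospitalized as a result of an event that occurs there. The fourth limb of the definition therefore does little work between admission and discharge, when perioperative complications arise. With no limb for a longer stay or for intervention, a complication that keeps the patient in hospital or returns the patient to theatre can be classed as non-serious.

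What is at stake is how fast the sponsor, IRBs, regulators and other investigators hear of such events, and whether they are classed alike. This is an FDA-ordered surveillance study with safety as a stated purpose and subsequent surgery among its endpoints. If some of the up to 12 centers read the hospitalization limb as covering a prolonged stay and others do not, SAE classification will also differ between centers.

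**Working it through.** No formula or planned figure is involved. The check is to read the provisions against each other and run typical events through them.

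**Step 1: routes to a 24-hour report.** IV.G gives three: the event is an SAE, it is a UADE, or it is of unexpected severity.

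**Step 2: the SAE route.** It has four limbs. Death, threat to life and disability apply wherever the patient is. The hospitalization limb catches a new admission. No other section adds a limb for a prolonged stay or for surgery.

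**Step 3: the UADE route.** It starts from "any serious adverse effect on health or safety, or any life-threatening problem or death caused by, or associated with, a device", but only where the effect was not already identified in nature, severity or degree of incidence, or is otherwise unanticipated. Section 2.3 of the Dynesys Instructions for Use already lists, among others, "Nerve damage, including loss of neurologic function, dural tears, paralysis, paresthesia, and cerebral spinal fluid leakage", infection, loosening and loss of fixation, and warns that corrective surgery may follow. That section gives types only, with no severities or rates. A listed type can therefore still qualify if its severity or incidence is out of line. A listed complication of the expected kind does not.

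**Step 4: the unexpected-severity route.** A complication of expected severity does not meet it.

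**Step 5: apply the rules.**

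| Event | SAE? | 24-hour report? |
|---|---|---|
| Fatal, life-threatening or disabling complication in the index stay | Yes | Yes |
| Listed complication, unexpectedly severe | Only if a limb is met | Yes |
| Unanticipated serious device effect | Only if a limb is met | Yes, as a UADE |
| Dural tear of expected severity, repaired, longer stay, no disability | No | No |
| Return to theatre in the same admission to reposition a screw, anticipated and of expected severity, no disability | No | No |
| Later reoperation with a new admission | Yes | Yes |
| Later adverse-event-driven procedure without admission, anticipated and of expected severity, no disability | No | No |

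The screw case is a revision under IV.G, which covers adjusting the position of the implant. The three rows ending in No are the gap.

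**Step 6: what happens to those events.** Item 14 of the Operative/Discharge Evaluation asks "Were there any intraoperative or immediate postoperative complications"; a Yes sends the site to the adverse event form, with no 24-hour instruction there. Section IV.K asks for CRFs within 15 days of evaluation. The 24-hour limit runs from when the investigator learns of the event, so the two clocks start at different points and the delay cannot be stated as a fixed number of days. Monitoring is required at least once every 12 months (VI.E). A later adjudication cannot restore a 24-hour report.

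**Step 7: size.** Up to 168 subjects have an index stay. One percent of subjects is 0.01 × 168 = 1.68. The documents give no rate to multiply by.

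**The case against.** The case against rests on several points, most of which limit the concern without removing it.

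- **The other limbs and routes.** A reader might infer that only hospitalization counts, or that every serious in-hospital complication escapes the 24-hour rule. The text does not support either. Three limbs apply at the bedside as anywhere else, and UADEs and events of unexpected severity are reported within 24 hours. Nor does listing in the Instructions for Use make an event expected in severity. Nerve damage with paralysis, though listed, can meet the disability limb directly.
- **The safety results.** A reader might infer that the reported safety profile is understated. Section V.C specifies no SAE rate. It analyses adverse events by incidence, severity and time course, secondary surgeries by type, incidence and time course, and tests non-inferiority by AE category. All adverse events are recorded whatever their severity, and additional surgeries are described in the treatment narrative. This objection stands: the planned analyses do not depend on the SAE label.
- **Lost events.** These events are not lost to the sponsor. The 15-day CRF timeline applies, so the sponsor learns of them later. This also stands.
- **Severe but not serious.** A reader might call this a contradiction. It is not: IV.H has the adjudicators decide severity and seriousness separately. The point is only that the severity grade does not fill the gap.
- **A count of affected subjects.** Assuming that 3% to 10% of subjects have such an event would give about 5 to 17 of 168 (0.03 × 168 = 5.0; 0.10 × 168 = 16.8). Nothing in the documents anchors that range, so it should not be read as an estimate.
- **The unseen form.** The adverse event CRF is not in the available text, and its seriousness fields could not be checked. If it lists further criteria, sites may apply them in practice, but the form would then differ from the definition in IV.G.

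**Conclusion.** The point holds in limited form. As worded, IV.G leaves two groups of events outside SAE status unless they are fatal, life-threatening or disabling: anticipated complications of expected severity during the index admission, and adverse-event-driven repeat procedures without a new admission. Where such a procedure is also anticipated and of expected severity, no other route brings it into the 24-hour report. The harm is to expedited reporting and to SAE classification. AE capture, the fusion analysis and the planned safety analyses are unaffected.

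The number of events cannot be stated; the exposure is up to 168 index stays plus any later procedure without admission. The conclusion assumes that the hospitalization limb is read literally, as causing an admission, and that no document outside the available text widens it. The definition is worth amending because these are perioperative events in a study whose purpose is safety, and the change is small.

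**What to change.** Amend the definition in IV.G so that an SAE also includes an adverse event that (a) prolongs an existing hospitalization, or (b) leads to surgical intervention, meaning revision, removal, reoperation or supplemental fixation as IV.G already defines them, whether or not there is a new admission. Leave out elective removal after fusion, which IV.G already treats as reportable but not an adverse event. State in IV.H that the adjudicators use the same definition, and check that the adverse event CRF matches it. The admission and discharge dates in items 1 and 2 of the Operative/Discharge Evaluation can support the check for prolongation, so no new data item is needed for that.

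The change takes one sentence in IV.G and a cross-reference in IV.H. The downside is some additional 24-hour reports and IRB notices, and a slightly higher SAE count. The sample size and the analyses in Section V do not change.
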